7.0 TREATMENT PLAN

Drug	Dose ^c	Frequency	Route of Administration
Daratumumab	16 mg/kg body weight	Weekly, weeks 1-8	IV infusion
Daratumumab	16 mg/kg body weight	Every 2 weeks, weeks 9-24 ^a	IV infusion
Daratumumab	16 mg/kg body weight	Every 4 weeks, week 25 ^b onwards, for up to 24 months of total study therapy	IV infusion

^a First dose of the every-2-week dosing schedule is given at week 9

^b First dose of the every-4-week dosing schedule is given at week 25

^c Weight from screening visit will be used for initial dosing and throughout treatment period but will be recalculated for weight change $\geq 10\%$.

Infusion rates for daratumumab administration

	Dilution volume	Initial rate (1 st hour)	Rate increment ^a	Maximum rate
First infusion	1000 mL	50 mL/hour	50 mL/hour every hour	200 mL/hour
Second infusion ^b	500 mL	50 mL/hour	50 mL/hour every hour	200 mL/hour
Subsequent infusion ^c	500 mL	100 mL/hour	50 mL/hour every hour	200 mL/hour

^a Consider incremental escalation of the infusion rate only in the absence of infusion reactions.

^b Use a dilution volume of 500 mL only if there were no Grade 1 (mild) or greater infusion reactions during the first 3 hours of the first infusion. Otherwise, continue to use a dilution volume of 1000 mL and instructions for the first infusion.

^c Use a modified initial rate for subsequent infusions (i.e. third infusion onwards) only if there were no Grade 1 (mild) or greater infusion reactions during a final infusion rate of ≥ 100 mL/hr in the first two infusions. Otherwise, continue to use instructions for the second infusion.

7.1 Week 1 and Week 2 infusions (i.e., the first two doses)

The following premedications should be administered approximately 30-60 minutes prior to infusion

- Acetaminophen 650 mg po
- Diphenhydramine 25-50 mg po/iv
- Methylprednisolone 100 mg iv for first two doses (C1 D1 and C1 D8)
- Loratadine 10 mg po
- Famotidine 20 mg iv
- Montelukast 10 mg po
- Ondansetron 4mg iv

The following should be administered at the 2 hour infusion point, (even if there is no reaction)

- Diphenhydramine 25 mg po/iv
- Famotidine 20 mg iv
- Methylprednisolone 40 mg iv

The following medications should be administered post-infusion to reduce the risk of delayed infusion reactions:

- Methylprednisolone 20 mg (or equivalent) orally for 2 days, 24 and 48 hours following the infusion start time
- Montelukast 10 mg orally for 2 days, 24 and 48 hours following the infusion start time (only for first 4 infusions)

7.2 ALL subsequent doses (i.e. starting with week 3 dose):

The following premedications should be administered approximately 30-60 minutes prior to infusion.

- Acetaminophen 650 mg po
- Diphenhydramine 25-50 mg po/iv or Claritin 10 mg po
- Methylprednisolone 60 mg iv
- Famotidine 20 mg iv
- Ondansetron 4mg iv (as needed)
- Montelukast po 10 mg (optional following the first dose)

The following medications should be administered post-infusion to reduce the risk of delayed infusion reactions:

- Methylprednisolone 20 mg (or equivalent) orally for 2 days, 24 and 48 hours following the infusion start time
- Montelukast 10 mg orally for 2 days, 24 and 48 hours following the infusion start time (only for first 4 infusions) (optional)

7.3 Additional Information

Patients with a history of chronic obstructive disease or asthma will undergo pulmonary function testing for the determination of their forced expiratory volume in one second (FEV1) prior to daratumumab exposure. In addition, this population of patients should be considered for short and long-acting bronchodilators in addition to inhaled corticosteroids post-infusion.

Patients will be initiated on antiviral prophylaxis (acyclovir or valacyclovir) to prevent herpes zoster reactivation within one week of starting daratumumab and will be continued for 3 months following the completion of treatment.

Daratumumab binds to CD38 on red blood cells (RBCs) and results in a positive Indirect Antiglobulin Test (Coombs test). Daratumumab-mediated positive indirect antiglobulin test may persist for up to 6 months after the last daratumumab infusion. Daratumumab bound to

RBCs can mask detection of antibodies to minor antigens in the patient's serum. The determination of a patient's ABO and Rh blood type are not impacted. Blood bank must be notified if a patient has received daratumumab and of this interference with serological testing. Order type and screen and blood bank phenotype on patients prior to starting daratumumab.

HBV Serology:

All subjects will be tested locally for hepatitis B surface antigen (HBsAg), hepatitis B surface antibody (Anti-HBs), and hepatitis B core antibody (Anti-HBc) at Screening. Additionally, subjects ongoing in the Treatment Phase who are within 6 months of starting study treatment when Protocol Amendment v11.0 is implemented will be required to have HBV serology performed locally upon signing the updated ICF.

HBV serology is not required at Screening or for subjects ongoing in the Treatment Phase who are within 6 months of starting study treatment if this was performed as part of standard of care within 3 months prior to first dose.

HBV DNA tests:

Subjects who are positive for Anti-HBc or Anti-HBs will undergo testing for hepatitis B DNA by PCR. Subjects with serologic findings suggestive of HBV vaccination (Anti-HBs positivity as the only serologic marker) and a known history of prior HBV vaccination do not need to be tested for HBV DNA by PCR. During and following study treatment, subjects who have history of HBV infection will be closely monitored for clinical and laboratory signs of reactivation of HBV as specified in the Time and Events Schedule (Section 9). Where required by local law, the results of HBV testing may be reported to the local health authorities

Management of Hepatitis B Virus Reactivation:

Primary antiviral prophylaxis is permitted as per local standard of care. Per protocol, HBV DNA testing by PCR is mandatory for subjects at risk for HBV reactivation. For subjects who are diagnosed with HBV reactivation while on treatment, study treatment should be interrupted until the infection is adequately controlled. If the benefits outweigh the risks, study treatment may be resumed with concomitant antiviral prophylaxis as per local standard of care. Consult a liver disease specialist as clinically indicated.

7.4 Criteria For Removal From Protocol Treatment:

- 7.4.1 Hematologic progression of disease.
- 7.4.2 Organ progression in the absence of hematologic response
- 7.4.3 Complete hematologic response, with continuation of the study drug per the discretion of the treating investigator
- 7.4.4 Unacceptable toxicity.
- 7.4.5 The patient may withdraw from the study at any time for any reason.
- 7.4.6 Development of overt multiple myeloma.
- 7.4.7 Completion of 24 months of daratumumab.

- 7.5 All patients will be followed until initiation of next treatment.

8.0 **TOXICITIES TO BE MONITORED AND DOSAGE MODIFICATIONS**

See Section 3.0 for potential toxicities associated with daratumumab. In all patients experiencing such toxicities, an attempt should be made to distinguish between drug toxicity, associated medical illness, or disease (amyloid)-related symptomology.

Dose delay is the primary method for managing daratumumab-related toxicities.

Infusion-related reactions:

Infusion reactions of any grade will lead to the temporary interruption or slowing of the infusion, as well as management of symptoms. Depending on the grade/severity of the reaction, this may require the permanent discontinuation of the drug.

For Grade 1-2 infusion reactions, daratumumab can be resumed at half the rate at which the reaction occurred. Further escalation of the rate is still possible providing the patient does not experience any further reactions.

For Grade 3 reactions, the infusion can be restarted at half the rate once the intensity of the reaction has decreased to a Grade 2 level or lower. Further escalation of the rate is still possible providing the patient does not experience any further reactions. The above instructions can be repeated if another Grade 3 reaction occurs. Permanent discontinuation of daratumumab should be undertaken if a third Grade 3 or greater reaction occurs.

For Grade 4 reactions (life threatening), daratumumab should be discontinued permanently.

Non-reaction Daratumumab-Related Toxicity Management

The criteria for a dose delay are:

- Grade 4 hematologic toxicities
- Grade 3 thrombocytopenia with bleeding
- Febrile neutropenia of any grade
- Neutropenia with infection, of any grade
- Grade 3 or higher non-hematologic toxicities with the following exceptions:
 - Grade 3 nausea that responds to antiemetic treatment within 7 days
 - Grade 3 vomiting that responds to antiemetic treatment within 7 days
 - Grade 3 diarrhea that responds to antidiarrheal treatment within 7 days
 - Grade 3 fatigue that was present at baseline or that lasts for <7 days after the last administration of daratumumab
 - Grade 3 asthenia that was present at baseline or that lasts for <7 days after the last administration of daratumumab

Daratumumab Delays

Administration of daratumumab may be restarted upon recovery from toxicity to Grade 2 or baseline, with the exception that Grade 2 laryngeal edema or Grade 2 bronchospasm must be fully recovered. If more than 2 consecutive planned doses of daratumumab are missed due to adverse events, treatment should be permanently discontinued. If 2 consecutive doses of daratumumab are missed for any reason other than adverse events, this should be brought to the attention of the Sponsor at the earliest possible time and study treatment should be discontinued, unless, upon consultation with the sponsor and the review of data, continuation is agreed upon.

No dosage adjustments are required for patients with pre-existing renal dysfunction. According to prior pharmacokinetic studies, no dosage adjustments are required for mild hepatic dysfunction (Total Bili 1.0-1.5x ULN or AST > ULN). Daratumumab has not been studied in patients with moderate or severe hepatic dysfunction (Total Bili > 1.5 x ULN). These patients will be excluded from the study (see exclusion criteria section 5.2).

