Infusion rates for daratumumab administration:

	Dilution volume	Initial rate (1 st hour)	Rate increment ^a	Maximum rate
First infusion	1000 mL	50 mL/hour	50 mL/hour every hour	200 mL/hour
Second infusion ^b	500 mL	50 mL/hour	50 mL/hour every hour	200 mL/hour
Subsequent infusion ^c	500 mL	100 mL/hour	50 mL/hour every hour	200 mL/hour

^a Consider incremental escalation of the infusion rate only in the absence of infusion reactions.

^b Use a dilution volume of 500 mL only if there were no Grade 1 (mild) or greater infusion reactions during the first 3 hours of the first infusion. Otherwise, continue to use a dilution volume of 1000 mL and instructions for the first infusion.

^c Use a modified initial rate for subsequent infusions (i.e. third infusion onwards) only if there were no Grade 1 (mild) or greater infusion reactions during a final infusion rate of ≥ 100 mL/hr in the first two infusions. Otherwise, continue to use instructions for the second infusion.

Daratumumab will be administered at the FDA-approved dose of 16mg/kg as an intravenous infusion. Weight from screening visit will be used for initial dosing and throughout treatment period but will be recalculated for weight change $\geq 10\%$. It will be administered weekly from weeks 1 to 8, followed by every 2 weeks from weeks 9 to 24, and then every 4 weeks thereafter until progression or unacceptable toxicities, for up to 24 months of total study therapy.

The first infusion of daratumumab (in 1000 mL) will be administered at an initial rate of 50 mL/hour to be escalated hourly by 50 mL/hour to a maximum rate of 200 mL/hour.

The second infusion of daratumumab will be administered in 500 mL if no grade 1 or greater reactions have occurred throughout the first 3 hours of the first infusion. The second infusion will be administered at an initial rate of 50 mL/hour to be escalated hourly by 50 mL/hour to a maximum rate of 200 mL/hour

The third and subsequent doses will be administered in 500 mL at a starting rate of 100 mL/hour to be escalated hourly by 50 mL/hour to a maximum rate of 200 mL/hour as long as no \geq Grade 1 infusion reactions occur during a final infusion rate of ≥ 100 mL/hr in the first two infusions.

Infusion reactions of any grade will lead to the temporary interruption or slowing of the infusion, as well as management of symptoms. Depending on the grade/severity of the reaction, this may require the permanent discontinuation of the drug.

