5.0 RECRUITMENT AND CONSENTING

The investigators will recruit participants from within their own practice. It is standard of care that patients scheduled for visits within the hematology/oncology clinics are "pre-screened" to determine if they may be "potentially eligible" for any available clinical trials. This is not specific for this study.

A screening consent is not obtained, as the pre-screening review is conducted prior to their appointment.

No data will be collected. The medical records are reviewed and a screening note is placed in the medical record to indicate that the patient may or may not be "potentially eligible" for a clinical trial. If the patient is potentially eligible, the physician will discuss the study at the visit. No procedures are performed for screening until after consent is obtained.

No data will be retained prior to obtaining consent. No data is collected during the "pre-screening". During the pre-screen, if a patient is determined to be not potentially eligible for any available clinical trials, the patient would not be considered as a "screen fail" as they have not undergone a full screening.

If potentially eligible, the investigator will inform the potential participant within his/her practice that he/she may be eligible for the research study. If the patient agrees to discuss and receive information about the study, an IRB-approved Informed Consent Form will be presented to the patient by a member of the research staff who will verbally outline the details of the procedures, risks, benefits, alternatives, costs, etc. The patient will be given the opportunity to bring the consent home and discuss with family members and/or other physicians and to ask any and all questions of the investigator and/or research staff. Once the patient is satisfied that all questions have been answered, if he/she wishes to participate, the consent form will be signed and dated by the patient and the person obtaining consent. Copies of the signed Informed Consent Form will be given to the patient and placed in the appropriate medical record. The original copy will be placed in the research chart.

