6.0 ELIGIBILITY CRITERIA

6.1 Eligibility Criteria

- Histological diagnosis of primary systemic (AL) amyloidosis:
 - a. At least one tissue demonstrating positive Congo Red staining with characteristic apple green birefringence AND/OR characteristic appearance of fibrils on electron microscopy **AND**
 - b. Evidence of a clonal plasma cell dyscrasia:
 - i. Monoclonal protein in the serum and/or urine by immunofixation electrophoresis **AND/OR**
 - ii. Abnormal serum free light chain assay **AND/OR**
 - iii. Clonal plasma cell population in the bone marrow demonstrated by immunohistochemistry, flow cytometry or in situ hybridization **AND**
 - c. Evidence of organ involvement other than carpal tunnel syndrome. Confirmation of tissue diagnosis at all sites of organ dysfunction is encouraged, but not required.
- Must have received at least one prior treatment regimen of proven efficacy in the treatment of AL amyloidosis. If prior treatment included ASCT, at least 6 months must have elapsed between ASCT and study drug.
- Must be ≥ 18 years of age.
- Must have a performance status of 0-2 by ECOG criteria (see Section 10.4)
- Must have adequate hepatic function as evidenced by serum bilirubin values < 2.0 mg/dL; ALT and/or AST $< 3 \times \text{ULN}$ (bilirubin < 3 mg/dL allowed if related to Gilbert's syndrome).
- Must have an absolute neutrophil count $\geq 1000/\text{mm}^3$, hemoglobin ≥ 7.5 g/dL, and platelet count $\geq 50 \times 10^9/\text{L}$

6.2 Exclusion Criteria:

- Renal Insufficiency (CrCL $< 20 \text{ mL/min}$), calculated by Cockcroft-Gault Equation
$$\text{CreatClear} = \text{Sex} * ((140 - \text{Age}) / (\text{SerumCreat})) * (\text{Weight} / 72)$$

*Equation parameters such as **Sex** have two or more discrete values that may be used in the calculation. The numbers in the parentheses, e.g. (1), represent the values that will be used.*

The default unit of measure for weight is kilograms. Please verify that the correct unit of measure has been selected.

<http://reference.medscape.com/calculator/creatinine-clearance-cockcroft-gault>
- Mayo clinic cardiac biomarker stage IIIb (see appendix 14.3)
- Evidence of significant cardiovascular conditions as specified below:
 - NT-ProBNP > 8500 ng/L (Mayo Stage IIIb patients are excluded)

- New York Heart Association (NYHA) classification IIIB or IV heart failure (see Section 10.5)

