9.0 STUDY CALENDAR

	Screening	Prior to each dose	Monthly (CxD1)	Every 3 Month beginning C4,D1	End of Study Treatment Visit ⁵
PHYSICAL⁹					
History & Physical Exam, including liver assessment	X		X ⁷	X	X
Height	X				
ECOG Performance Status (see 10.4)	X	X		X	X
Vital Signs & Weight		X		X	
Adverse Event Monitoring		X		X	X
SF-36 (QOL)	X			X	
LABORATORY-Serum					
Complete Blood Count with Differential	X	X		X	X
Beta-HCG ¹	X				
Chemistry including: BUN, creatinine, glucose, sodium, potassium, chloride, bicarb, cholesterol, CK, calcium, total protein, LDH, magnesium, phosphorous, triglycerides, uric acid, TSH, amylase	X	X		X	X
BUN / Serum Creatinine	X	X		X	X
Creatinine Clearance ³	X				
Hepatic Function Testing: ALT/AST, Bilirubin, Albumin, Alkaline Phosphatase	X	X		X	X
β-2 Microglobulin / C-reactive protein	X			X	X
Cardiac enzymes: BNP/ Troponin I/NT ProBNP	X	X		X	X
Serum free light chain assay	X	X ⁸		X	X
SPEP, SIFE, Immunoglobulins	X			X	X
Coombs test; IAT (anti globulin test)	X				
Coagulation profile: PTT, INR, D-dimer, Factor X	X			X	X
HBV serology testing ¹⁰	X				
HBV DNA testing ¹¹	X				X
Type And Screen and blood bank phenotype ⁶	X				
Daratumumab-specific Immunofixation (patients with Kappa disease only)	X			X	X
LABORATORY-Urine					
Urinalysis	X			X	X
24 hour urine: total protein, creatinine, kappa, and lambda	X			X	X
UPEP / UIFE / TV	X			X	X
PATHOLOGY					
BM biopsy	X ²				
Fat aspirate (if not previously done)	X				
X-RAYS AND SCANS					
ECG / CXR	X				
Echocardiogram	X			Every 6 months	
PFTs (required for chronic smokers or known COPD)	X				

1 For women of childbearing potential only.

2 Bone marrow biopsy and aspiration must have been repeated following any previous therapy > 1 cycle.

3 CreatClear = Sex * ((140 - Age) / (SerumCreat)) * (Weight / 72); Equation parameters such as Sex have two or more discrete values that may be used in the calculation. The numbers in the parentheses, e.g. (1), represent the values that will be used. The default unit of measure for weight is kilograms. Please verify that the correct unit of measure has been selected. <http://reference.medscape.com/calculator/creatinine-clearance-cockcroft-gault>

4 While on study drug or until disease progression or start of another therapy.

5 30 days following last dose (+/-) 7 days.

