10.0 CRITERIA FOR EVALUATION AND ENDPOINT DEFINITIONS

Patients will not be required to have a delta FLC of 40 mg/L for study entry as primary endpoint of the study is to evaluate safety and tolerability of the study drug. Hematologic responses will be assessed by other hematologic measures of disease including M-spike and presence of clonal plasma cells in the bone marrow. Organ responses will be assessed by changes in 24 hour protein excretion for patients with renal involvement; by changes in NT-proBNP for patients with cardiac involvement; and by changes in alkaline phosphatase levels and liver span for patients with hepatic involvement.

10.1 Toxicities:

Safety of the study drug will be assessed by using vital sign information in addition to data pertaining to the duration of therapy, interruption of therapy, routine laboratory assessments, and frequency and severity of AEs

10.2 Responses:

It is important to note that daratumumab is an IgGk monoclonal antibody that can be detected as an individual monoclonal band on SPEP and serum immunofixation electrophoresis (IFE). It can be confused with the endogenous IgG-k M-protein of the patient during IFE interpretation. Co-migration can introduce a bias in M-protein quantification and can also mask clearance of the patient's M-protein by IFE. For optimal M-spike monitoring, our laboratory specialist will be informed if a patient is receiving daratumumab.

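### Section 8 excludes patients with total bilirubin above 1.5 x ULN, but the exclusion list in 6.2 has no such item, and the bilirubin limits in 6.1 can admit some of them

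*Combined protocol and SAP*

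**What the plan says.** The closing paragraph of Section 8.0 (Toxicities to be Monitored and Dosage Modifications) requires no dose adjustment for mild hepatic dysfunction. It then states: "Daratumumab has not been studied in patients with moderate or severe hepatic dysfunction (Total Bili > 1.5 x ULN"). The next sentence is an eligibility rule: "These patients will be excluded from the study (see exclusion criteria section 5.2"). It names no exception.

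The section it points to is titled "5.0 RECRUITMENT AND CONSENTING" and has no subsection 5.2. The exclusion criteria are in 6.2, where the only liver-related items are hepatitis B and hepatitis C.

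Bilirubin appears in Section 6 only as an inclusion criterion in 6.1: "Must have adequate hepatic function as evidenced by serum bilirubin values < 2.0 mg/dL", with the allowance "bilirubin < 3 mg/dL allowed if related to Gilbert's syndrome". The same item limits ALT and/or AST to below 3 x ULN. Both bilirubin limits are absolute values, whereas Section 8 uses a multiple of ULN. No laboratory ULN for bilirubin is given anywhere.

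**The concern.** Section 8 announces an exclusion and refers the reader elsewhere for it, and it is not there. Staff who screen from Section 6, where eligibility criteria are normally checked, would not see the 1.5 x ULN rule. By following Section 6 faithfully they could enrol a patient whom the protocol says is excluded because the drug has not been studied at that level of liver function.

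For patients with Gilbert's syndrome the two sections disagree outright: 6.1 allows them up to 3 mg/dL, and Section 8 excludes anyone above 1.5 x ULN.

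Safety and tolerability is the primary objective, and Section 10.0 expects some patients with liver disease, since organ response is to be assessed "by changes in alkaline phosphatase levels and liver span for patients with hepatic involvement". Raised bilirubin at screening is therefore not a remote possibility.

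**Working it through.** The plan gives no figure to reproduce. The check is whether the limits in 6.1 imply the limit in Section 8.

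**Inputs**
- Section 8 excludes total bilirubin > 1.5 x ULN.
- Section 6.1 admits bilirubin < 2.0 mg/dL, or < 3 mg/dL with Gilbert's syndrome.
- ULN is not stated. It is an assumption here, varied from 1.0 to 2.0 mg/dL.

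**Break-even ULN.** Section 6.1 admits someone whom Section 8 excludes when 1.5 x ULN is below the 6.1 limit.
- Without Gilbert's: ULN < 2.0 / 1.5 = 1.33 mg/dL.
- With Gilbert's: ULN < 3.0 / 1.5 = 2.0 mg/dL.

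**Width of the band open under Section 6 but closed by Section 8.** Width = max(0, 6.1 limit − 1.5 x ULN), in mg/dL.

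| Assumed ULN | 1.5 x ULN | Band without Gilbert's | Band with Gilbert's |
|---|---|---|---|
| 1.0 | 1.50 | 0.50 | 1.50 |
| 1.1 | 1.65 | 0.35 | 1.35 |
| 1.2 | 1.80 | 0.20 | 1.20 |
| 1.3 | 1.95 | 0.05 | 1.05 |
| 1.4 | 2.10 | 0 | 0.90 |
| 1.5 | 2.25 | 0 | 0.75 |
| 2.0 | 3.00 | 0 | 0 |

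**Example without Gilbert's.** At ULN 1.2, a patient at 1.9 mg/dL is at 1.9 / 1.2 = 1.58 x ULN. That patient passes the 6.1 bilirubin limit, meets no hepatic-function exclusion in 6.2, and is excluded by Section 8.

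**Does correcting the section number cure it?** Section 4.0 carries the same outdated pointer to 5.2, for stage IIIb cardiac disease. Reading that as 6.2 works, because 6.2 lists stage IIIb and NT-proBNP > 8500 ng/L. Reading the Section 8 pointer as 6.2 leads to a list without the criterion.

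**Entry limit if the Section 8 rule is added to 6.2 and 6.1 is kept.** Without Gilbert's, the limit is min(2.0, 1.5 x ULN) = 1.50, 1.65, 1.80, 1.95, 2.00 and 2.00 mg/dL at ULN 1.0, 1.1, 1.2, 1.3, 1.4 and 1.5. It never exceeds the present 2.0. Replacing the 6.1 limit by 1.5 x ULN would instead raise it to 2.10 at ULN 1.4 and 2.25 at ULN 1.5, looser by 0.10 and 0.25.

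**The case against.** The strongest reply is that hepatic eligibility is largely handled already. Section 6.1 bars anyone without Gilbert's syndrome at 2.0 mg/dL or above and limits transaminases. What remains is a band at most 0.50 mg/dL wide over the assumed ULNs of 1.0 to 1.3, and no band at 1.34 or above. For these patients both rules can be obeyed together, and Section 8 is part of the same protocol, so a mistake requires staff to screen from Section 6 alone. All of this stands, and it limits the consequence. It does not put the announced rule into the exclusion list.

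A second reply is that the documents do not show which threshold is intended, so 6.1 could simply govern. That would remove the inconsistency, but it would override an explicit exclusion and admit a group that the protocol itself calls unstudied. The argument has real force for Gilbert's syndrome: the 6.1 allowance looks deliberate, and writing it into Section 8 loosens that section's literal wording. The sponsor has to settle that.

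A reader might also infer that the trial would expose patients to a known hepatic hazard. The documents do not support this. Section 8 reports an absence of data, not a toxicity signal. These patients would follow the same plan as everyone else ("Daratumumab will be administered at the FDA-approved dose of 16mg/kg as an intravenous infusion") under the same delay rules. The Study Calendar schedules "Hepatic Function Testing: ALT/AST, Bilirubin, Albumin, Alkaline Phosphatase" at screening and before each dose.

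**Conclusion.** The inconsistency is real and its safety consequence is minor. Section 8 states an exclusion that 6.2 does not contain, and 6.1 does not reproduce it.

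- **Without Gilbert's syndrome:** Section 6 can admit patients whom Section 8 excludes only if the ULN is below 1.33 mg/dL. At assumed ULNs of 1.0, 1.1, 1.2 and 1.3 they are those above 1.50, 1.65, 1.80 and 1.95 mg/dL respectively, and below 2.0.
- **With Gilbert's syndrome:** 6.1 and Section 8 contradict each other at any ULN below 2.0 mg/dL, for example from above 1.80 to below 3.0 mg/dL at ULN 1.2.

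Two stronger conclusions would go too far. One is that excluded patients will be, or were, enrolled in some number: with no ULN and no bilirubin distribution in the documents, the number among the 25 planned cannot be estimated. The other is that the results are affected. Section 11.3 plans descriptive summaries without hypothesis tests and uses everyone who received a dose for both safety and efficacy, so no sample size or planned analysis changes.

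**What to change.** 1. Add to 6.2: *Total bilirubin > 1.5 x ULN (except Gilbert's syndrome with bilirubin < 3 mg/dL).*
2. Keep < 2.0 mg/dL in 6.1, so that entry without Gilbert's syndrome is governed by the lower of 2.0 mg/dL and 1.5 x ULN.
3. Have Section 8 cite 6.1 and 6.2 and name the same Gilbert's exception. The sponsor should first confirm that the 6.1 allowance is intended. If it is not, remove it from 6.1 and leave the exception out of 6.2 and Section 8.

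The cost is protocol wording only. The downside is that, where the ULN is below 1.33 mg/dL, a few patients between 1.5 x ULN and 2.0 mg/dL become ineligible under Section 6, as Section 8 already states. Some of them may have hepatic involvement and could otherwise have contributed to the organ-response assessment.
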